2.1.1.5 On-treatment assessments

Safety summaries (tables, figures) include only data from the on-treatment period defined below, with the exception of baseline data, which will also be summarized where appropriate (e.g., change from baseline summaries). In addition, a separate summary for death, including on-treatment and post-treatment deaths, will be provided. Summary tables for AEs will include only on-treatment events, with a start date during the on-treatment period (*treatment-emergent AEs*), as discussed in [Section 2.8.2.1.2](#).

The overall observation period will be divided, for safety assessments, into three mutually exclusive segments as follows:

Pre-treatment period: from the day of patient’s first informed consent to the day before first administration of the study treatment.

On-treatment period: from date of first administration of study treatment to 30 days after the date of last actual administration of VAY736 (including start and stop date).

Post-treatment period: starting at day 31 after last administration of VAY736.

If dates are incomplete in a way that clear assignment to pre-, on-, post-treatment period cannot be made, then the respective data will be assigned to the on-treatment period.

Note that these observational period definitions do not impact the reporting of efficacy assessments; all completed efficacy assessments will be summarized, irrespective of their timing with regard to the above definitions.

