7.1.1 Screening

Screening starts after a patient has provided written informed consent to participate in the study and ends on the day of the first dose of VAY736 and ibrutinib. Screening assessments have to be done within 21 days prior to the first dose with the exception of baseline tumor assessments and informed consent. Screening tumor assessments collection can be conducted within 28 days of first dose and informed consent can be obtained within 3 months of the first dose. Assessments conducted prior to obtaining informed consent as a part of routine disease care can be used to satisfy eligible criteria as long as the procedures were performed within the allowed windows.

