5. Whether medication or therapy was given (no concomitant medication/non-drug therapy, concomitant medication/non-drug therapy)
6. Outcome (not recovered/not resolved, recovered/resolved, recovered/resolved, recovered/resolved with sequelae, fatal, unknown).

If the event worsens the event should be reported a second time in the CRF noting the start date when the event worsens in toxicity. For grade 3 and 4 adverse events only, if improvement to a lower grade is determined a new entry for this event should be reported in the CRF noting the start date when the event improved from having been Grade 3 or Grade 4.

All adverse events should be treated appropriately. If a concomitant medication or non-drug therapy is given, this action should be recorded on the Adverse Event CRF.

Once an adverse event is detected, it should be followed until its resolution or until it is judged to be permanent, and assessment should be made at each visit (or more frequently, if necessary) of any changes in severity, the suspected relationship to the study treatment, the interventions required to treat it, and the outcome.

[figure not shown]
Progression of malignancy (including fatal outcomes), if documented by use of appropriate disease assessment method (IWCLL), should not be reported as a serious adverse event.

Adverse events separate from the progression of malignancy (example, deep vein thrombosis at the time of progression or hemoptysis concurrent with finding of disease progression) will be reported as per usual guidelines used for such events with proper attribution regarding relatedness to the drug.

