10.5.3.2 Adverse events (AEs)

Summary tables for adverse events (AEs) will include only AEs that started or worsened during the on-treatment period, the treatment-emergent AEs.

The incidence of treatment-emergent adverse events (new or worsening from baseline) will be summarized by system organ class and or preferred term, severity (based on CTCAE grades), type of adverse event, relation to study treatment.

Serious adverse events and non-serious adverse events will be tabulated.

All deaths (on-treatment and post-treatment) will be summarized.

All AEs, deaths and serious adverse events (including those from the pre and post-treatment periods) will be listed and those collected during the pre-treatment and post-treatment period will be flagged.

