2.8.2.1.2 Data analysis

AE Summaries (CSR outputs)

AE summaries will include only AEs that started or worsened during the on-treatment period, the treatment-emergent AEs. All AEs collected in the AE (e)CRF page will be listed along with

the information collected on those AEs e.g., AE relationship to study drug, AE outcome etc. AEs starting during the post-treatment period will be flagged in the listings.

AEs will be summarized by number and percentage of patients having at least one AE, having at least one AE in each primary system organ class (SOC) and for each preferred term (PT) using MedDRA coding. A patient with multiple occurrences of an AE will be counted only once in the respective AE category. A patient with multiple CTCAE grades for the same preferred term will be summarized under the maximum CTCAE grade recorded for the event. AE with missing CTCAE grade will be included in the 'All grades' column of the summary tables.

In AE summaries the primary system organ class will be presented alphabetically, and the preferred terms will be sorted within primary SOC in descending frequency. The sort order for the preferred term will be based on their frequency in the investigational arm.

The following adverse event summaries will be produced by treatment:

- Overview of adverse events (number and % of patients with any AE, any SAE any fatal SAE, any dose reductions/interruptions, AE leading to discontinuation, AE requiring additional therapy);

The following adverse event summaries will be produced by treatment and maximum grade (All grades and Grade ≥ 3):

- AEs by SOC and PT, regardless of relationship to study treatment and suspected to be related to study treatment;
- Serious adverse events by SOC and PT, regardless of relationship to study treatment and suspected to be related to study treatment Leading to treatment discontinuation;
- AEs leading to dose interruption/adjustment;
- AEs Requiring additional therapy;
- Dose limiting toxicities by SOC and PT;

The following listings will be produced:

- All adverse events (safety set)

Deaths (CSR Outputs)

Separate summaries for on-treatment and all deaths (including post-treatment death) will be produced by treatment arm, system organ class (SOC) and preferred term (PT).

All deaths will be listed for the safety set, and post-treatment deaths will be flagged.

The death summaries cover patients from the Safety Set.

EudraCT and clinicaltrials.gov requirements for AEs and Deaths summaries

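### SAP 2.1.1.5 selects treatment-emergent AEs by start date, so the CRF entry opened when a pre-treatment Grade 3-4 AE improves on treatment meets the rule although the event is neither new nor worse

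*SAP*

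**What the plan says.** Five statements bear on this.

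- SAP 2.1.1.5 defines the on-treatment period as running "from date of first administration of study treatment to 30 days after the date of last actual administration of VAY736". It then states that "Summary tables for AEs will include only on-treatment events, with a start date during the on-treatment period", labels these treatment-emergent, and points to SAP 2.8.2.1.2.
- SAP 2.8.2.1.2 puts it differently: "AE summaries will include only AEs that started or worsened during the on-treatment period".
- Protocol 10.5.3.2 sets the standard against baseline: "The incidence of treatment-emergent adverse events (new or worsening from baseline) will be summarized".
- Protocol 8.1.1 governs how entries are made. A worsening is entered again, dated when it worsened. Improvement is also entered again for severe events: "For grade 3 and 4 adverse events only, if improvement to a lower grade is determined a new entry for this event should be reported", "noting the start date when the event improved from having been Grade 3 or Grade 4".
- AEs are recorded from consent (Protocol 8.1.1), and under Protocol 7.1.1 "informed consent can be obtained within 3 months of the first dose". Entries dated before first dose can therefore exist. Conditions already present at consent go to Medical History instead.

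**The concern.** The date on an improvement entry is the date of recovery, not of onset. A rule that looks only at entry dates cannot tell a recovery from a new event or a worsening. The incidence and severity of AEs is a primary endpoint (Protocol Table 3-1, SAP Table 1-1), and the error can run in only one direction: a recovery is presented as an event that arose on the combination. Severity can be affected too, because SAP 2.8.2.1.2 tabulates all grades and Grade 3 or higher, and an entry that improves from Grade 4 to Grade 3 would fall in the second group.

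**Working it through.** The plan gives no figure that depends on this rule, so the check applies the two definitions to hypothetical entries made as Protocol 8.1.1 requires. First dose is day 1, and pre-dose entries are dated day -6.

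- Rule S (SAP 2.1.1.5): any entry with a start date on or after day 1 is treatment-emergent.
- Rule W (SAP 2.8.2.1.2 with Protocol 10.5.3.2): the event is treatment-emergent only if it is new, or if its grade on treatment exceeds its last pre-dose grade.

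| Course of the event | Rule S | Rule W |
|---|---|---|
| Grade 3 pre-dose, improves to Grade 2 on day 5 | Yes, shown at Grade 2 | No |
| Grade 4 pre-dose, improves to Grade 3 on day 5 | Yes, shown at Grade 3 | No |
| Grade 2 pre-dose, worsens to Grade 3 on day 5 | Yes | Yes |
| Grade 2 pre-dose, improves to Grade 1 | No (no new entry is made) | No |
| New Grade 2 on day 5 | Yes | Yes |

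The rules differ only for improvement entries of Grade 3-4 events.

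**Can SAP 2.1.1.5 be read so that it works?** There are two ways to read its start date.

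1. As the date of each CRF entry. Worsenings are then captured, as SAP 2.8.2.1.2 requires, but so are improvements.
2. As the onset date of the event. Improvements then drop out, but so do worsenings of events that began before first dose, against SAP 2.8.2.1.2 and Protocol 10.5.3.2.

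Neither reading gives the protocol's definition without a comparison of grades, and the SAP text states no such comparison for AEs.

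**Does another rule remove the entry?** SAP 2.8.2.1.2 merges consecutive entries of the same term separated by no more than 1 day, but only for occurrence counts in the registry tables. It does not decide treatment emergence. The visible items in SAP Section 4 (changes from the protocol) do not mention the definition.

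**Size.** A patient is counted once per term (SAP 2.8.2.1.2), so a false entry adds to a term's incidence only if that patient has no genuine on-treatment event of the same term. The addition is then 100/n percentage points, where n is the size of the dose-and-schedule group, because safety data are pooled that way (Protocol Section 10, SAP 2.1). For illustration:

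- n = 20: 100/20 = 5.0 points
- n = 15: 100/15 = 6.7 points

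The documents do not give the number of affected patients.

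**The case against.** The strongest reply is that the intent is already clear. The sentence in SAP 2.1.1.5 refers the reader to 2.8.2.1.2, which requires an event to have started or worsened on treatment, and the protocol measures that from baseline. Protocol 8.1.1 treats the improvement as a further entry for the same event, so it is not a new AE. Derivations are also specified in a separate programming document (SAP Section 1) that is not available here and may contain the missing rule. This stands as far as it goes. It shows that misclassification is a risk that depends on programming. A reader might infer that such events will certainly be counted, and the documents do not support that. But the intent does not make the written start-date rule correct, and nothing visible in the SAP says how to recognise or link an improvement entry.

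A reader might also infer that cytopenias at entry will generate many false events, since Protocol 5.2 admits an ANC from 0.75 and platelets from 25 x 10^9/L. The documents do not support this either:

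- A condition present at consent goes to Medical History and has no AE entry to split, unless it worsens after consent.
- Laboratory abnormalities are AEs only if clinically significant, symptomatic, or needing therapy or a change in study medication (Protocol 8.1.1).
- Grade 4 is below 0.5 for neutrophils and below 25 for platelets (SAP 5.3), so the eligibility limits nearly close the Grade 4 route for these two. The allowance in Protocol 5.2 for CLL-related cytopenias is the remaining gap.
- Laboratory grades are also reported separately as shifts from baseline (SAP 2.8.2.3.1), which this does not touch.

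Finally, it is tempting to use 26 patients (15 in escalation plus 11 then on treatment in expansion, at Amendment 6) as the denominator. That is an enrolment status with expansion still open, and safety tables are built by dose and schedule, so 26 is not an analysis denominator.

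**Conclusion.** SAP 2.1.1.5 is wrong as written, and the matter is minor. Its start-date rule, combined with the CRF rule in Protocol 8.1.1, admits a Grade 3-4 AE that began or worsened after consent, was still Grade 3-4 at first dose, and improved on treatment. That conflicts with SAP 2.8.2.1.2 and Protocol 10.5.3.2, and no rule visible in the SAP excludes it.

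The consequence is confined to that narrow class of events. A Grade 3 event that improves would inflate only the all-grades column; a false Grade 3 or higher count needs a pre-dose Grade 4 AE that improves to Grade 3. The size cannot be fixed from the documents. The 5.0 and 6.7 points above are per affected patient, assume groups of 20 and 15, and assume no genuine on-treatment event of the same term. Whether any table is actually wrong depends on the programming and on whether such events occurred.

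**What to change.** State the same rule in SAP 2.1.1.5 and 2.8.2.1.2:

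- Entries of the same event are linked. The same-term, gap of at most 1 day rule already used for the registry counts could serve.
- An on-treatment entry is treatment-emergent only if the event is new, or if its grade exceeds the last grade recorded before first dose.
- An entry opened only because a pre-treatment Grade 3-4 event improved is not treatment-emergent.

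The comparison should be with the last pre-dose grade, not with the immediately preceding entry. Otherwise a pre-dose Grade 3 event that falls to Grade 2 on day 5 and returns to Grade 3 on day 10 would count as emergent, although it was never worse than at baseline.

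The cost is a sentence or two in the SAP, a matching line in the programming specifications, and one derivation using dates and grades already collected. No new data and no protocol amendment are needed, since Protocol 10.5.3.2 already states the intended definition.

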2.1.1.6 Date of last contact date

The last contact date will be derived for patients not known to have died at the analysis cut-off date using the last complete date reported among the following as seen in [Table 2-1](#):

Table 2-1 Last contact derivation

Source data	Conditions
Last contact date/last date patient was known to be alive from Safety Follow-up page	Patient status is reported to be alive, lost to follow-up, or unknown
Start/End dates from further antineoplastic therapy	Non-missing medication/procedure term
Start/End dates from treatment page	Non-missing dose. Doses of 0 are allowed
End of treatment date from end of treatment page	No condition
Efficacy assessment date if available	Evaluation is marked as 'done'
Laboratory/Concomitant medication collection dates	Sample collection marked as 'done'
Vital signs date	At least one non-missing parameter value
Start/End dates of AE	Non-missing verbatim term

The last contact date is defined as the latest complete date from the above list on or before the data cut-off date. The cut-off date will not be used for last contact date unless the patient was seen or contacted on that date. No date post cut-off date will be used. Completely imputed dates (e.g., the analysis cut-off date programmatically imputed to replace the missing end date of a dose administration record) will not be used to derive the last contact date.

2.1.1.7 Date of start of alternative cancer therapy

The date of start of alternative cancer therapy is the Start Date of Dose as recorded on the Antineoplastic Therapy Since Discontinuation of Study Treatment – Medication eCRF. Note: The start date of Ibrutinib is not considered as the start of alternative cancer therapy.

2.2 Analysis Set/ Subject Classification/ Withdrawal of ICF/ Subgroups

2.2.1 Analysis sets

Full Analysis Set (FAS)

The Full Analysis Set (FAS) and Safety Set (SS) are defined in the same way and comprise all patients who received at least one dose of study treatment. Patients will be analyzed according to the study treatment received where treatment received is defined as the treatment most frequently taken between Study Day 1 and the end of cycle 1 (the first 28 days of dosing), the onset of a DLT, or treatment discontinuation, whichever occurs first.

Safety Set (SS)

Same as definition of FAS.

Per-Protocol Set (PPS)

Not applicable

Dose-Determining Set (DDS)

The Dose-Determining Set (DDS) includes all patients from the FAS (escalation part) who met the minimum exposure criterion and had sufficient safety evaluations or experienced a dose limiting toxicity (DLT) during cycle 1 (the first 28 days of dosing).

A patient has met the minimum exposure criterion if the patient takes, during the first 28 days, all planned doses of VAY736 and 75% of the planned doses of ibrutinib (i.e., two doses of VAY736 Q2W or one dose of VAY736 Q4W, and ≥ 21 of 28 daily doses of ibrutinib).

Patients who do not experience a DLT during cycle 1 (the first 28 days of dosing) are considered to have sufficient safety evaluations if they have been observed for ≥ 28 days following the first dose and are considered by both the Sponsor and Investigators to have enough safety data to conclude that a DLT did not occur. Patients will be analyzed according to the study treatment received as defined for FAS.

Patients who do not meet these minimum safety evaluation requirements will be regarded as ineligible for the DDS and an additional patient may be recruited (see [VAY736Y2102-CSP-Section 7.1.3.1](#)).

Pharmacokinetic Analysis Set (PAS)

The Pharmacokinetic Analysis Set (PAS) includes all Patients who provide an evaluable PK profile. A profile is considered evaluable if all the following conditions are satisfied:

- Patient receives one of the planned treatments.
- Patient provides at least one primary PK parameter (see [Table 2-7](#) for a listing)
- Patient did not vomit within 4 hours after the dosing of ibrutinib.

Immunogenicity Prevalence Set (IGPS)

The IGPS includes all patients in the FAS with a non-missing baseline IG sample **or** at least one non-missing post-baseline IG sample (applicable for VAY736 only)

Immunogenicity Incidence Set (IGIS)

The IGIS includes all patients in the IGPS with a non-missing baseline IG sample **and** at least one non-missing post-baseline IG sample (applicable for VAY736 only).

See [Section 2.8.4.5.2](#) for further definitions.

2.2.2 Subject Classification

Patients may be excluded from the analysis populations defined above based on the protocol deviations (PD) entered in the database and/or on specific classification rules defined in [Table 2-2 Classification based on PDs and non-PD criteria](#).

Table 2-2 Classification based on PDs and non-PD criteria

Analysis set	Protocol deviations leading to exclusion	Non protocol deviation leading to exclusion
Full analysis set	No written informed consent (INCL01)	Patient didn't receive at least one dose of study treatment
Safety set	No written informed consent (INCL01)	Patient didn't receive at least one dose of study treatment
Dose-determining set	No written informed consent (INCL01)	
1. The patient does not experience a DLT during the first cycle and does not meet the minimum exposure criterion.2. The patient does not experience a DLT during the first cycle but has no sufficient safety evaluation (i.e. he has not been observed for the full duration of the first cycle of treatment, and/or is considered by both Novartis and Investigators to have not enough safety data to conclude that a DLT did not occur).
PK Analysis set	No written informed consent (INCL01)	
1. Patient didn't receive at least one of the planned treatments2. Patient didn't provide at least one primary PK parameter3. Patient vomited within 4 hours after the dosing of ibrutinib
Immunogenicity prevalence set	No written informed consent (INCL01)	Patients without a determinant baseline IG sample or at least one

		determinant post-baseline IG sample
Immunogenicity incidence set	No written informed consent (INCL01)	Patients without a determinant baseline IG sample and at least one determinant post-baseline IG sample

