2.8.4 Pharmacokinetic analysis

PK parameters will be determined using non-compartmental method(s) for VAY736 and ibrutinib. PK parameters such as those listed in [Table 2-7](#) will be estimated and reported, when applicable. For ibrutinib, PK parameters determined will be only AUClast, Cmax, Tmax, Tlast, and if applicable other PK parameters (eg AUC0-t). The PAS subset of patients will be used in all pharmacokinetic data analysis and summary statistics.

Table 2-7 Noncompartmental pharmacokinetic parameters

AUClast	The AUC from time zero to the last measurable concentration sampling time (tlast) (mass x time x volume ⁻¹)
AUCinf	The AUC from time zero to infinity (mass x time x volume ⁻¹)
AUCtau	The AUC calculated to the end of a dosing interval (tau) after first dose and at steady-state (amount x time x volume ⁻¹)
Cmax	The maximum (peak) observed plasma, blood, serum, or other body fluid drug concentration after single dose administration (mass x volume ⁻¹)
Tmax	The time to reach maximum (peak) plasma, blood, serum, or other body fluid drug concentration after single dose administration (time)
T1/2	The elimination half-life associated with the terminal slope (λ_z) of a semi logarithmic concentration-time curve (time). Use qualifier for other half-lives
CL/F	The total body clearance of drug from the plasma (volume x time ⁻¹)
Vz/F	The apparent volume of distribution during terminal phase (associated with λ_z) (volume)
Racc	Accumulation ratio should be calculated using AUC values obtained from a dosing interval

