2.8.4.2 Data analysis set

All pharmacokinetic data analyses and PK summary statistics will be based on PAS. Only PK blood samples with date and time and for which the last prior dose dates and times are adequately recorded will be included in the PK analyses.

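### The ibrutinib vomiting criterion in the shared PK analysis set is not limited to ibrutinib, so valid intravenous VAY736 profiles can be dropped

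*SAP*

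**What the plan says.** SAP Section 2.2.1 builds the PAS from profiles: "The Pharmacokinetic Analysis Set (PAS) includes all Patients who provide an evaluable PK profile". It continues: "A profile is considered evaluable if all the following conditions are satisfied". The third condition is "Patient did not vomit within 4 hours after the dosing of ibrutinib". It names no analyte and does not say which ibrutinib dose counts.

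Table 2-2 in Section 2.2.2 restates the three conditions as reasons for leaving a patient out, the third being "Patient vomited within 4 hours after the dosing of ibrutinib". The lead-in is permissive: "Patients may be excluded from the analysis populations defined above".

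Section 2.8.4 covers both drugs: "PK parameters will be determined using non-compartmental method(s) for VAY736 and ibrutinib". It then says "The PAS subset of patients will be used in all pharmacokinetic data analysis and summary statistics", and Section 2.8.4.2 repeats the point: "All pharmacokinetic data analyses and PK summary statistics will be based on PAS". Section 2.8.4.1 adds that concentration data may be left out of the estimation of certain parameters, with vomiting among the possible reasons.

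Protocol Section 10.1.5 has the same undivided condition with an 8-hour window. SAP Section 4, item 6, records the change to 4 hours and justifies it for ibrutinib only.

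**The concern.** A vomiting rule protects the PK of an oral drug, because part of the dose may never be absorbed. VAY736 is infused. A rule that makes its profiles depend on whether an ibrutinib tablet or capsule stayed down discards data and protects nothing.

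At stake is the VAY736 half of a secondary objective (PK of both drugs in combination) and the dose-proportionality analysis of VAY736 AUC and Cmax in SAP Section 2.8.4.4. Both rest on escalation cohorts of 3 to 6 patients, where each profile carries weight.

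**Working it through.** **1. Is there another set for VAY736 PK?** No. Sections 2.8.4 and 2.8.4.2 send all PK of both drugs to the PAS. The SAP does restrict sets by drug where it means to: the two immunogenicity sets in Section 2.2.1 are marked as applying to VAY736 only. The PAS carries no such mark.

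**2. What does each place do with a patient who vomits within 4 hours of an ibrutinib dose?**

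| Place | Unit | Effect on VAY736, read literally |
|---|---|---|
| 2.2.1 | profile | the VAY736 profile linked to that dosing day fails one of the required conditions; other profiles can still qualify |
| Table 2-2 (2.2.2) | patient | the patient may be excluded, and with the patient every VAY736 profile |
| 2.8.4.1 | concentration data, certain parameters | further removal is possible; an excluded patient is not brought back |

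The three do not agree, and none exempts VAY736.

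**3. Does the criterion have a purpose for VAY736?** Protocol Table 6-1 and Section 6.1.1 give ibrutinib orally and VAY736 intravenously. Protocol Section 1.3.3 expects little interaction and no shared clearance pathway. That vomiting leaves VAY736 exposure unchanged is inferred from these facts; the documents do not state it.

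**4. Where do the sampling schedules meet?** Protocol Tables 7-6 to 7-8 start serial sampling of both drugs on C1D1, so an episode that day touches a VAY736 profile on either SAP unit. On C3D1, the start of the full VAY736 profile, ibrutinib is sampled pre-dose only. An episode after that dose cannot affect that day's ibrutinib sample, yet it could make the VAY736 profile unevaluable.

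**5. What does one exclusion cost?** The share of a cohort of n that is lost is 1/n: 1/3 = 33%, 1/4 = 25%, 1/5 = 20%, 1/6 = 17%. With the same standard deviation, the standard error of a cohort mean grows by √(n/(n−1)): √(3/2) = 1.225 for n = 3 and √(6/5) = 1.095 for n = 6.

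**6. How often might it happen?** The documents give no vomiting rate and no figure to reproduce, so this is illustration only. Assume a chance p of a qualifying episode per dose, independent across k relevant days. The chance of at least one is 1 − (1 − p)^k.

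| Days counted | k | p = 0.1% | p = 0.5% | p = 1% |
|---|---|---|---|---|
| Serial ibrutinib sampling (C1D1, C1D8) | 2 | 0.2% | 1.0% | 2.0% |
| All scheduled ibrutinib sampling days (C1D1, D2, D8; D1 of C2 to C8: 3 + 7) | 10 | 1.0% | 4.9% | 9.6% |

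For the 15 escalation patients given in the Amendment 06 study status, the expected number affected runs from 15 × 0.002 = 0.03 to 15 × 0.096 = 1.4.

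**The case against.** The case for leaving the text alone is reasonable. Section 2.2.1 is the definition, and it works by profile. Table 2-2 appears to summarise it under a permissive lead-in. On that view a patient with another clean profile stays in the PAS. Section 2.8.4.1 would be largely redundant if one episode had already removed the patient, which also suggests that finer handling was intended. Patients must be taking and tolerating ibrutinib at entry (protocol 5.1), and uncontrolled vomiting that may significantly alter absorption is excluded (protocol 5.3, criterion 18). The PK analyses are descriptive, dose proportionality is optional, immunogenicity has its own sets, and no primary endpoint is involved.

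Most of this stands, and it rules out three stronger readings that a reader might infer:

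- **One episode is certain to remove the patient from all PK.** The profile wording in 2.2.1 and the permissive lead-in in 2.2.2 do not support certainty.
- **Any of 8 × 28 = 224 daily ibrutinib doses could trigger the rule.** The SAP criterion names no day, but a 4-hour window needs a recorded vomiting time, and protocol 6.1.1.1 and 7.2.3.1 ask for that only on sampling days.
- **A sizeable, selective loss of patients with gastrointestinal toxicity.** No vomiting rate is given, so neither its size nor its selectivity can be shown.

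What the objection does not meet is the missing analyte limit. Even by profile, the vomiting condition applies to VAY736. Section 2.8.4.1 can only remove more data, and discretion at the time of analysis is weaker than a stated rule.

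**Conclusion.** The point holds as a defect of definition. The PAS applies an ibrutinib-specific criterion to both drugs, in two places with different units, so valid VAY736 profiles can be dropped without a stated reason. How many is unknown and may be few or none; the rates in the working are assumptions. What follows from the design alone is the cost of each exclusion: 33% of a cohort of 3, or 17% of a cohort of 6. The conclusion rests on the inference that vomiting an oral dose does not alter exposure to an infused antibody. It does not depend on the vomiting rate, because the criterion serves no purpose for VAY736 at any rate.

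**What to change.** Make four changes in the SAP:

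1. In 2.2.1, define PAS evaluability by analyte and by profile.
2. Apply the vomiting criterion only to post-dose ibrutinib samples or profiles following the affected dose. Do not apply it to VAY736 or to the patient's other ibrutinib profiles.
3. Reword the PK row of Table 2-2 in 2.2.2 to the same unit, and align both places with 2.8.4.1 so that vomiting is handled by one rule.
4. Record the change in Section 4, item 6, which already revises this criterion, since protocol 10.1.5 has the same undivided condition.

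The cost is a few lines of text and an analyte-level flag in the PK dataset, made by amendment before database lock or addendum after it, as SAP Section 1 provides. No new data are needed, and ibrutinib PK keeps its protection. This is a free improvement.
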